#### 4.2.4 Immunological data

The rules for handling BLQ or ALQ measurements for all immunological data will be as described in Section 4.2.2.

Descriptive statistics will be calculated if at most 33% of the individual data points at a timepoint are missing or are either not quantifiable (<LLOQ) or ALQ as described in Section 4.2.2.

#### 4.2.5 Rozanolixizumab concentration data

Measurements that are BLQ will be imputed with half of the LLOQ for the purpose of calculating the geoMean and its 95% CI, the geoCV, the arithmetic mean, and SD for summaries and figures. If any summary value (geoMean, arithmetic mean, lower CI level or minimum) is lower than LLOQ, then 'BLQ' will be displayed.

For the individual figures, any concentrations that are BLQ will be considered as missing, with the exception of predose BLQ measurements on Day 1, which will be imputed with zero for linear scale plots.

Additional rules for PK data summaries are provided in Section 9.1.

#### 4.2.6 Electrocardiogram data

For the ECG data, all calculations of changes from Baseline and descriptive statistics will be based on the mean of the triplicate assessments at each timepoint. In the event that there are not 3 available measurements at a given timepoint, the mean will be calculated based on the number of measurements for which data is provided.

#### 4.2.7 Dates and Times

Partial dates may be imputed for the following reasons:

- Classification of AEs as treatment-emergent
- Classification of medications and procedures as prior or concomitant
- Derivation of time to use of rescue medication

Imputed dates will not be shown in the listings; all dates will be displayed as reported in the database.

The following rules will be applied for partial start dates:

- If only the month and year are specified and the month and year of dosing is not the same as the month and year of the start date then use the 1st of the month, or the date of Screening if this is later
- If only the month and year are specified and the month and year of dosing is the same as the month and year of the start date, then use the date of dosing. If this results in an imputed start date that is after the specified end date, then use the 1st of the month, or the date of Screening if this is later
- If only the year is specified, and the year of dosing is not the same as the year of the start date then use January 01 of the year of the start date, or the date of Screening if this is later

- If only the year is specified, and the year of dosing is the same as the year of the start date, then use the date of dosing. If this results in an imputed start date that is after the specified end date, then use January 01 of the year of the start date, or the date of Screening if this is later
- If the start date is completely unknown, then use the date of dosing. If this results in an imputed start date that is after the specified end date, then use January 01 of the year of the end date, or the date of Screening if this is later.

Missing start times will be imputed as 00:00h or with the time of dosing for events occurring on the date of IMP administration in case of missing hour and minute. Otherwise start times with only missing minutes will be imputed with :00.

Start and end time is not recorded for concomitant medications, thus no imputations for missing times will be performed. Any medication with a start date on the first dosing date, will be assumed to be concomitant.

The following rules will be applied for partial stop dates:

- If only the month and year are specified, then use the last day of the month;
- If only the year is specified, then use December 31 of the known year;
- If the stop date is completely unknown, do not impute the stop date

Missing or partially missing date and/or times will be imputed as described in [Table 4–1](#) for the calculation of duration of each AE. Adverse event duration is computed in and reported in day and time format: xx d hh:mm.

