#### **3.5.4 Full Analysis Set**

The Full Analysis Set (FAS) will consist of all participants in the SS, who have a Baseline and at least one valid post-Baseline iRODS measurement up to Visit 17/PEOT (inclusively).

Measurements are considered invalid if the participant received rescue medication before the assessment of iRODS. Assessments collected at the same day as first intake of rescue medication are considered valid. Invalid measurements will not be used for summary tables and MMRM, but kept in listings.

The FAS is the primary analysis set for efficacy analyses. In the case of mistreatment, participants will be analyzed as treated if the participant received the incorrect treatment for the entire study period. In the case of partial mistreatment, patients should be analyzed as randomized, but considered as protocol violators. As for the SS, in the case of mistreatment participants will be primarily analyzed as treated. However, if applicable, sensitivity analyses will also be performed according to the randomized treatment group.

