### 8.2.9 Use of rescue medication

The percentage of participants with concomitant medication identified as rescue medication [Yes/No] in the eCRF and time to first rescue medication administration will be summarized by treatment group and for all participants and listed by treatment group at each scheduled assessment during the Treatment and Observation Period.

If a participant receives rescue medication at multiple times, the relative day of the first occurrence is used to define the time to rescue medication.

The statistical methods applied to use of rescue medication and time to use of rescue medication will be the same as for CIDP relapse (iRODS), see Sections 8.2.1 and 8.2.1.1. The rule for handling missing data is described in Section 4.2.7.

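### One early-date rule for partial start dates also sets time to rescue, which it can only shorten, and the SAP does not say which date decides whether an assessment is valid when the rescue date is partial

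*SAP*

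**What the plan says.** SAP 4.2.7 names three reasons for completing a partial date: deciding whether an adverse event is treatment-emergent, sorting medications and procedures into prior or concomitant, and "Derivation of time to use of rescue medication". The same start-date rules serve all three.

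- Nothing known: "If the start date is completely unknown, then use the date of dosing".
- Year only: where it is known "and the year of dosing is the same as the year of the start date, then use the date of dosing"; otherwise 1 January of that year.
- Month and year, in the dosing month: the date of dosing.
- Month and year, in any other month: "then use the 1st of the month, or the date of Screening if this is later".

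The section adds: "Imputed dates will not be shown in the listings; all dates will be displayed as reported in the database".

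SAP 8.2.9 takes the relative day of the first rescue as the time to rescue, applies the Kaplan-Meier methods of 8.2.1.1, and says "The rule for handling missing data is described in Section 4.2.7".

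A separate rule in SAP 3.5.4 reads: "Measurements are considered invalid if the participant received rescue medication before the assessment of iRODS". Same-day assessments count as valid, and FAS membership needs at least one valid post-Baseline iRODS. SAP 3.9, 4.2.1 and 8 repeat the validity rule. None of them refers to 4.2.7 or says what to do when the rescue date is incomplete.

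**The concern.** Choosing the earliest plausible start date suits adverse events, because SAP 10.2 treats an event with an unclear date as treatment-emergent unless there is evidence against it. Time to rescue is a named efficacy variable, and there the same choice pushes every incomplete date in one direction.

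The imputed value can also contradict data already held. Protocol 6.4 requires IMP to stop once a subject is treated with rescue medication in the Treatment Period. A rescue dated to Day 1 in someone who went on to receive infusions is therefore inconsistent with that person's dosing record. The rule makes no use of the last IMP dose, the relapse visit or the PEOT date.

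There is also a gap. Assessment validity turns on when rescue first began, and no rule covers a partial rescue date for that purpose. A programmer would have to reuse the 4.2.7 date or devise something else. Reusing it could flag genuine pre-rescue iRODS values as invalid.

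**Working it through.** **Inputs.** The start-date rules are those of SAP 4.2.7. Time to rescue is counted from the start of treatment, following SAP 8.2.1.1, whose methods 8.2.9 adopts. Post-Baseline iRODS is scheduled weekly on nominal Days 8, 15, ..., 85, which is 12 visits (Protocol Table 5-1). Infusions fall on nominal Days 1, 8, ..., 78. The date of dosing is not defined for a 12-dose trial. I read it as the first dose, because the same section refers to the first dosing date when it classifies concomitant medication.

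**Formula.** Day = date − date of first infusion + 1.

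**Example (assumed first dose 5 May).**
- 28 May: 23 + 1 = Day 24.
- 29 June: 26 days left in May + 29 + 1 = Day 56.
- 1 June: 26 + 1 + 1 = Day 28.

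| Recorded as | True day | Imputed day | Shift (days) | iRODS visits on or before the true day | On or before the imputed day |
|---|---|---|---|---|---|
| May | 24 | 1 | 23 | 3 | 0 |
| June | 56 | 28 | 28 | 7 | 3 |
| Year only, or nothing (true date 29 June) | 56 | 1 | 55 | 7 | 0 |

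The last two columns matter only if the imputed date is also used for validity, which the SAP does not state.

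**Conflict with dosing.** In the first row, infusions on Days 8, 15 and 22 follow the imputed rescue. In the second, infusions on Days 29, 36, 43 and 50 do. Neither sequence is possible if the discontinuation rule was followed.

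**Range.** I applied the rules to every first-dose date in 2019 and every true rescue day from 9 to 85, weighted equally. The uniform timing is an assumption.
- Month-only: mean shift 14 days, maximum 30; Day 1 in 11% of cases; up to 5 visits between imputed and true date.
- Year-only: mean shift 42 days, maximum 84; Day 1 in 87%.
- Unknown: mean shift 46 days, maximum 84; Day 1 in 100%; up to 12 visits.

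No case moves rescue later.

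**Effect on the curve.** With 15 per arm and no censoring, moving one event forward lowers that arm's curve by 1/15 = 6.7 percentage points between the imputed and the true day.

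**Effect on power, if a participant left the FAS.** The planning figure in SAP 2.4 is reproduced first: 15 per group, one-sided 5% t-test, effect size 0.93 gives 79.9% (stated 80%). Losing 1, 2 or 3 participants from one arm gives 78.6%, 77.2% and 75.5%.

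**The case against.** The strongest reply is that the consequence is narrow. Validity is not among the three listed purposes of imputation, and the validity rule never refers to 4.2.7. A reader might infer that the plan invalidates pre-rescue iRODS values and removes participants from the FAS. The documents do not say so, and that reading should not be treated as the plan's rule.

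Without that link, only the timing in one descriptive analysis is affected. SAP 8 calls all efficacy analyses exploratory and presents no p-values. Whether a participant had rescue at all does not depend on the imputed day. Someone given Ig rescue before Week 13 counts as relapsed whatever the exact day (SAP 4.2.1).

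Partial rescue dates may also be rare. Rescue is Ig started at relapse, tied to visits and identified in the eCRF; data checks are planned (Protocol 13.3.2); and the dates as reported stay visible in the listings.

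All of this stands, and it keeps the point small. It does not remove it. For time to rescue the rule is stated, it is cross-referenced, and it returns values that other data can contradict. The listings would show the partial date but not the date used.

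**Conclusion.** The point holds for time to rescue. The stated rule biases that variable in one direction, by about two weeks on average for month-only dates and by the whole interval since the first dose for unknown dates, under the assumed uniform timing. It can yield a rescue date before infusions that were actually given.

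For the primary analysis the finding is a gap. The SAP does not say which date sets the validity flag when a rescue date is partial. If the 4.2.7 date were reused, valid iRODS values could be lost, and a Day 1 date would leave no valid post-Baseline value and so remove the participant from the FAS. One such loss costs little power (79.9% to 78.6%); the worry is bias and an undocumented programming choice.

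The conclusion rests on reading the date of dosing as the first dose. The documents give no frequency of partial rescue dates; with none, there is no effect. A reader might also infer that the loss would fall mainly on placebo. That is plausible if rescue is commoner there, but the documents do not establish it. This is a low-priority correction.

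**What to change.** Take rescue medication out of the shared start-date rule in SAP 4.2.7 and give it its own.

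- Impute a partial rescue start within the recorded month or year and no earlier than the last IMP dose. Use the recorded relapse-visit date where it fits the known part of the date, and when nothing is known. If the relapse visit does not fit, name the admissible date that will be used.
- State separately that the validity flag does not use the 4.2.7 early date. Where the order of an assessment and rescue cannot be determined, PEOT included, analyse it both as valid and as invalid in a sensitivity analysis.
- Query partial rescue dates before lock, and flag any that remain imputed.

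Simply taking the latest possible date, or allowing none before PEOT, would be a poor substitute if that date also set validity. Rescue on 3 June recorded as June would become 30 June, so 27 days of post-rescue scores could enter as valid. SAP 4.2.1 also provides for rescue before PEOT and for same-day assessments being valid, so a floor at PEOT would admit PEOT values that the rule means to exclude.

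The cost is one or two SAP sentences, routine queries and a small sensitivity run. The floor at the last dose assumes that IMP stopped at rescue; a documented deviation should override it.

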## 10.2 Adverse events

Adverse events will be recorded from the time of informed consent until study completion. All AEs will be coded (Section 3.8) and categorized by relationship to rozanolixizumab.

In addition, AEs will be classified according to the Common Terminology Criteria for Adverse Events (CTCAE) Version 5.0 for severity. For any AEs where it is not possible to provide a CTCAE grading, the events will be assessed using a standard intensity classification (mild, moderate and severe).

A TEAE is defined as any event that was not present prior the first administration of IMP or any unresolved event already present before the first administration of IMP that worsens in intensity following exposure to treatment until 8 weeks following the last administration of IMP. Adverse events starting before the first administration of IMP or later than 8 weeks after the administration of the last IMP will not be considered TEAEs. Such events will be listed only.

Where dates are missing or partially missing, AEs will be assumed to be treatment-emergent unless evidence exists that does not allow the AE to be treatment-emergent. Handling of missing dates/times for classification of AEs as TEAEs is described in Section 4.2.7.

The following rules will be used to assign a TEAE to the study periods:

1. **Treatment Period:** a TEAE will be assigned to the Treatment Period for the tabulations if the start date/time of the event is at the time of or after the first administration of IMP on Day 1, up to Visit 17/PEOT (non-inclusively).
2. **Observation Period:** a TEAE will be assigned to the Observation Period for the tabulations if the start date/time of the event is at or after Visit 17/PEOT till 8 weeks after administration of the last IMP.
  - The Observation Period's TEAEs will be stratified by TEAEs of participants who received/did not receive standard of care treatment (i.e. Ig treatment) between start of the Observation Period and occurrence of the TEAE.

The number and percentage of participants who experience TEAEs will be summarized by Treatment Period, Observation Period (standard of care treatment status identified by WHODD J06BA01 and J06BA02) and Overall with respective treatment group. The following summaries will be presented:

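### SAP 4.2.7 sets missing minutes of an adverse-event start time to ':00' even in the hour of the first infusion, so an early Day 1 reaction may be dated before dosing and left out of the TEAE tables

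*SAP*

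**What the plan says.** SAP 4.2.7 names "Classification of AEs as treatment-emergent" among the purposes of its imputation rules. It then treats incomplete start times in two ways:

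- Hour and minute both missing: the start is set to midnight or, on a dosing day, "with the time of dosing for events occurring on the date of IMP administration in case of missing hour and minute".
- Hour present, minutes missing: "Otherwise start times with only missing minutes will be imputed with :00". No exception is made for the dosing day or the dosing hour.

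SAP 10.2 uses the resulting time. A TEAE belongs to the Treatment Period "if the start date/time of the event is at the time of or after the first administration of IMP on Day 1". Two groups are denied TEAE status, the 8 weeks being counted from the last dose: "Adverse events starting before the first administration of IMP or later than 8 weeks". For both groups the display rule is "Such events will be listed only".

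SAP 10.2 also has a presumption for events with missing or partly missing dates: "AEs will be assumed to be treatment-emergent unless evidence exists that does not allow the AE to be treatment-emergent". Its next sentence refers the handling of missing dates and times back to 4.2.7.

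**The concern.** The rule treats a better-documented record worse than a poorer one. On Day 1, an event with no start time is placed at dosing and counts as treatment-emergent. The same event with its hour known is rounded down and can land before dosing.

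At the first-dose boundary the error runs one way. Rounding down to the hour can move a post-dose onset to before dosing but cannot move a pre-dose onset to after it. Any effect on the tables is therefore to understate.

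The events exposed are those soon after the first infusion starts: infusion reactions, hypersensitivity, early headache. SAP 10.2 summarises all three as AEs of focus and defines AEs of focus as a kind of TEAE, so an event that loses TEAE status would leave those tables as well.

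The rule also departs from the SAP's own habit. Elsewhere in 4.2.7, partial start dates in the month or year of dosing normally take the dosing date, and a medication started on the first dosing date is assumed concomitant.

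**Working it through.** The documents give no figure for this rule, so there is none to reproduce. The check applies the rule as written.

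**Step 1. One example.** First infusion starts at 10:20 on Day 1; a reaction follows within the same clock hour.

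| Recorded start | Start under 4.2.7 | Relative to first dose | Literal result under 10.2 |
|---|---|---|---|
| 10:35 | 10:35 | 15 min after | TEAE |
| no time | 10:20 | at dosing | TEAE |
| 10:-- | 10:00 | 20 min before | not a TEAE, listed only |

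**Step 2. All infusion start minutes.** Let the infusion start at minute m of the hour (m = 0 to 59), with the event in that hour and its minutes missing. The imputed start is pre-dose when 0 < m, which is 59 of 60 values (98%). At m = 0 the times tie, and 10.2 counts a start at the time of dosing as treatment-emergent. With hour and minute both missing, the count is 0 of 60.

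**Step 3. Dependence on the delay (illustrative).** For a reaction d minutes after infusion start, misdating needs m > 0 and m + d ≤ 59, which is 59 − d start minutes, or none if d exceeds 59.

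| Delay d (min) | Misdated start minutes |
|---|---|
| 5 | 54 of 60 |
| 15 | 44 of 60 |
| 30 | 29 of 60 |
| 45 | 14 of 60 |
| 60 | 0 of 60 |

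If m is uniform over the hour and onset is uniform over the first T minutes, the misdated share is 1 − T/120 for T up to 60 and 30/T beyond that. This gives 75% for T = 30, 50% for T = 60 and 25% for T = 120. Every share here is conditional on the minutes being missing. The uniform distributions and the windows are assumptions, not figures from the documents.

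**Step 4. Size of one record.** With 34 randomised 1:1 there are 34/2 = 17 per arm, and 1/17 = 5.9 percentage points. This is the most that one participant can move one table row, and only if that participant has no other event counting in that row.

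**Step 5. After the change.** If a minutes-missing start in the hour of the first infusion takes the infusion start time, 0 of 60 start minutes give a pre-dose time, the same as the existing rule for a wholly missing time.

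**The case against.** A reader might infer that such an event certainly leaves the TEAE tables and that nothing later in the SAP corrects it. The documents do not settle that. SAP 10.2 presumes treatment emergence unless evidence rules it out, and an imputed ':00' is a placeholder rather than evidence of pre-dose onset. If the presumption reaches incomplete times, the event is kept. If it covers only dates, as worded, then 4.2.7 does not contradict it outright, because times are expressly sent there. This part of the objection stands. What remains is a literal rule that misdates the event, and two sections that can classify it differently depending on how the programmer reads them.

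A reader might also infer a material bias in the safety results. The documents do not support that either:

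- Protocol 7.2 requires the sequence of infusion-related events to be recorded accurately, and the first dose is given at the site with at least 4 hours of observation after the infusion (Protocol 8.2). Missing minutes should be uncommon.
- TEAE status depends on the first administration only, so the other 11 doses are unaffected.
- Participants are counted once per term. One who has the same term later still counts in that row of the overall table, and one with any other TEAE still counts under any TEAE.
- The AE listing covers all AEs, with onset and an infusion-reaction flag, so the event is not lost to review.

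These points limit the scale. They do not justify a rule that keeps the less complete record and may drop the more complete one.

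**Conclusion.** The point holds as a minor flaw in a stated derivation rule. Read literally, SAP 4.2.7 dates a post-dose Day 1 event before dosing when it falls in the clock hour in which the first infusion started and only its minutes are missing, for 59 of 60 infusion start minutes. The event may then be excluded from the TEAE and AE-of-focus tables. That is the literal outcome but not a certain one, because the reach of the presumption in 10.2 is unclear. The result conflicts with the conservative intent of 10.2.

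Events with a full start time, in a later clock hour, or at later infusions are not affected. The number of exposed records is not given and is probably small. The percentages are illustrative, and the 5.9 points is a ceiling for one participant in one row. Nothing in the documents shows that such a record exists or that the safety conclusions would change.

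**What to change.** Change both sections so that they agree.

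- **SAP 4.2.7:** state that if only the minutes are missing and the event starts on the date and in the same clock hour as the first IMP administration, the start time is imputed with the start time of that administration, unless other recorded information (for example an end time before dosing) shows pre-dose onset. All other minutes-missing start times stay at ':00'.
- **SAP 10.2:** word the treatment-emergent presumption for missing or partly missing dates or times, so that it no longer stops at dates. Changing 4.2.7 alone would leave that ambiguity in place.

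The cost is one sentence, a few words and one condition in the AE derivation program; no extra data are needed. The downside is that an occasional true pre-dose event in that hour would be counted as a TEAE. That is the conservative direction the SAP already takes for incomplete dates and for wholly missing times on a dosing day.
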